## **7.5 Complaint Handling**

All complaints will be handled in accordance with the Sengkang General Hospital Service Quality Department policy and aid. They will provide advice on the management strategies in such instances. If the complaint is related to a safety issue, the above (7.4) would apply.

# **8 DATA ANALYSIS**

## **8.1 Data Quality Assurance**

All data collected is prospective and the study team members and research administrators will convene to go through the peri-operative package, as well as the variables which are going to be

collected for the study. This will help standardise the method of assessment and finetune the method of administering the phone-based questionnaire.

All the study co-investigators would have also completed the CITI-training workshop and would be cognisant of the need for uniformity in terms of assessment of intraoperative and post-operative variables.

## **8.2 Data Entry and Storage**

Data will be entered into a data collection sheet by the study team or on the peri-operative package by the patient. All these data will be scanned in and images stored in a dedicated encrypted external hard-drive for archiving purposes. Hard-copy forms will be stored in a ring-file that is kept under lock-and-key by the PI. The data on the 2 data collection forms will be separately entered into an password-protected excel document, not having any patient identifiers, and stored in the dedicated encrypted hard-drive in a separate folder for the purposes of data analysis.

Only the study administrators and study co-investigators will have access rights for data entry and analysis though the PI.

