## **4 STUDY DESIGN**

This is a single-center, double-blind randomized controlled trial to be conducted in Sengkang General Hospital.

All patients presenting to the clinic or admitted for symptomatic haemorrhoids would be assessed for recruitment.

Figure 1 shows the enrolment process of the study population in the trial. Patients will be seen in the

clinic or in the wards for symptomatic haemorrhoids. All these patients would be approached and be introduced to this study but not recruited yet.

Patients older than 40 years-old with no recent colonoscopy (within 5 years) would need to have a colonoscopic evaluation of the colon after the index admission/clinic visit.

Those younger than 40 would be advised to have a rigid sigmoidoscopy on the day of the operation during the examination under anaesthesia. Only after agreement to the above, the patient would be recruited into the study. They would then be educated on the peri-operative questionnaire separately by a research administrator after recruitment into the trial.

The peri-operative package is split into pre- and post-operative components and will include basic demographics, baseline haemorrhoid-specific QoL questionnaires, VAS scales for POD0-10 and details of the intraoperative procedure and intraoperative description of the haemorrhoids.

Patients who fit the inclusion and exclusion criteria would be recruited into the study. We will perform a 1:1, block-of-4 randomization using a computer-generated programme performed by an independent research administrator who is not part of the surgical team.

They will be allocated only after they are examined under anaesthesia. Allocation is provided in a concealed opaque envelope that is provided by the research administrator on the day of the operation. Thus, the patient is blinded to the procedure. There will also be no cross-over from one study arm to another.

Potential Difficulties and Alternative Approaches to achieve the aims:

Difficulty of recruitment of patients into the trial may be potentially present especially for a procedure that is new in Singapore. Patient counselling and explanation of the procedure would be important and offering a short video clip of the procedure may be helpful. The procedurists/co-investigators of the study team would also be trained by a regional practitioner of the technique before the initiation of the trial to ensure proficiency for reassurance.

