#### **4.1 Randomisation and Blinding**

Patients who fit the inclusion and exclusion criteria would be recruited into the study. We will perform a 1:1, block-of-4 randomisation using a computer-generated programme performed by an independent research administrator who is not part of the surgical team.

They will be allocated only after they are examined under anaesthesia. Allocation is provided in a concealed opaque enveloped that is provided by the research administrator on the day of the operation. Thus, the patient is blinded to the procedure. There will also be no cross-over from one study arm to another.

An independent research administrator, not part of the randomisation process, will also contact the patient 3 months and 1 year after the procedure as mentioned above.

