### **9.2 Statistical and Analytical Plans**

#### **a. General Considerations**

All analysis would be conducted with the assistance or validation of a biostatistician. SPSS or Strata would be used to conduct the analysis. All categorical data would be analysed using the Fisher Exact Test. All continuous variables would be analysed using the Mann-Whitney U test. The level of statistical significance would be set as  $p < 0.05$ .

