## **12.1 Informed Consent**

Upon satisfaction of the inclusion and exclusion criteria, the primary surgeon (co-investigator) would introduce the trial to the patient in their preferred language either themselves or through a proxy. Upon interest, the research administrators will provide further details of the trial to the patient in a separate room in the clinic/wards. The patient will have ample time to read the patient information form (in the language that the patient can read) and consider enrolment into the trial. After the decision to participate, he/she would be invited to sign on the recruitment consent forms.

The research administrator and co-investigators would have to document the consult and the risks that of participation and of the techniques that were explained. In obtaining and documenting informed consent, the investigator should comply with the GCP guidelines and to the ethical principles that have their origin in the Declaration of Helsinki.

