## **12.2 Confidentiality of Data and Patient Records**

Data will be entered into a data collection sheet by the study team or on the peri-operative package by the patient. All these data will be scanned in and images stored in a dedicated encrypted external hard-drive for archiving purposes. Hard-copy forms will be stored in a ring-file that is kept under lock-and-key by the PI. The data on the 2 data collection forms will be separately entered into a password-protected excel document, not having any patient identifiers, and stored in the dedicated encrypted hard-drive in a separate folder for the purposes of data analysis.

Only the study administrators and study co-investigators will have access rights for data entry and analysis through the PI.

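### Operating surgeons, who know the arm of their own patients, hold data-entry and analysis rights over the primary VAS in a trial called double-blind

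*Protocol*

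**What the plan says.** **Access.** Section 8.2 states: "Only the study administrators and study co-investigators will have access rights for data entry and analysis though the PI". Section 12.2 gives the same rule, "Only the study administrators and study co-investigators will have access rights for data entry and analysis through the PI", and section 14 repeats it.

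**Who the co-investigators are.** Section 4 writes of "The procedurists/co-investigators of the study team would also be trained by a regional practitioner of the technique". Section 12.1 says that "the primary surgeon (co-investigator) would introduce the trial to the patient in their preferred language".

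**Allocation and blinding.** Section 4 declares: "This is a single-center, double-blind randomized controlled trial to be conducted in Sengkang General Hospital". On timing, section 4.1 says: "They will be allocated only after they are examined under anaesthesia". From this, sections 4, 4.1 and 6.5 conclude that the patient is blinded. They name no other blinded party. Sections 4.3.1 and 6.5 have the patient told the allocation at the clinic review 4 to 6 weeks after surgery.

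**Data path of the primary outcome.** Section 2.2 makes it the daily VAS over the first 10 days. Under section 4 the VAS sheets belong to a peri-operative package that also records the intraoperative procedure. Administrators collect it at the 4 to 6 week visit (4.3.1). Under section 8.2 forms are scanned and archived, the principal investigator keeps the paper locked away, and the data are typed into a password-protected Excel file without patient identifiers.

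**Statistician.** Section 9.2 a: "All analysis would be conducted with the assistance or validation of a biostatistician".

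**The concern.** In a pain trial whose surgeons cannot be blinded, protection comes from the patient's blinding and from keeping people who know the arm away from the handling of the primary outcome. The protocol secures the first. On the second, its access rule admits the surgeons to both entry and analysis.

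Two steps are exposed. One is transcription from paper to Excel, where an unclear or missing entry calls for judgement. The other is analysis: section 2.2 names ten daily scores, section 9.1 sizes the trial on the proportion scoring above 7.5, and the protocol does not say which day or summary is tested. An analyst who knows the arm would have room to choose, and section 2.1 states the expected direction of the result.

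What is at stake is the credibility of the primary comparison and the accuracy of the double-blind label. The concern is with the final data path, not the interim looks.

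**Working it through.** The point rests on reading sections against each other; no figure in the plan depends on it.

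1. **Are the co-investigators the operators?** Yes. Section 4 treats procedurists and co-investigators as one group, and section 12.1 calls the primary surgeon a co-investigator.
2. **Do they know the arm?** Allocation is revealed once the patient has been examined under anaesthesia (4, 4.1, 6.5), so whoever operates must learn it. Each surgeon is certain to know only their own cases. Knowledge can spread, because all study team members review every complication (7.4 and 9.2 b).
3. **Do they have rights over the VAS data?** Yes, for entry and for analysis, in three sections. The rule is permissive: no section says that surgeons will in fact enter the VAS.
4. **Is the arm hidden during entry or analysis?** No section says so. Removing patient identifiers does not hide the arm. The VAS and the procedure details sit in one package, so even an administrator who has not seen the allocation could see the procedure while entering scores.
5. **Is anyone kept independent?** The administrator who randomises is outside the surgical team (4, 4.1), and the one who telephones at 3 months and 1 year is outside the randomisation process (4.1). Nothing comparable covers entry or analysis of the 10-day VAS.
6. **Would a change be noticed?** It could be, because scans and originals exist. No comparison with them is stated, and the principal investigator controls both the paper and access to the file.
7. **Does the biostatistician have access?** The list is exclusive and does not name that role, while section 9.2 requires its assistance or validation throughout.

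**Can a size be given?** Only as an illustration on assumed data. Section 9.1's inputs (50% v 25%, 80% power, alpha 5% taken as two-sided) need 58 evaluable patients per arm by the pooled normal formula without continuity correction. With 58 per arm and the scores split at 7.5, the two-sided Fisher p-values for numbers above the cut (COH v LAH) are:

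| Above 7.5 | p |
|---|---|
| 29 v 20 | 0.132 |
| 30 v 19 | 0.060 |
| 30 v 18 | 0.038 |
| 31 v 18 | 0.024 |

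From that chosen start, moving one patient per arm does not cross 0.05; moving three or four in total, all in the same favourable direction, does.

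Section 9.2 assigns the Mann-Whitney test to continuous variables. Take the same start, 29 v 20 above 7.5, with scores assumed uniform on 3 to 7.5 and on 7.5 to 10. In 2,000 simulated data sets, moving two borderline patients per arm across 7.5 changed the median Mann-Whitney p from 0.150 to 0.134 and crossed 0.05 in about 3%. The Fisher table therefore describes a dichotomised analysis only and is not the size of this point.

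**The case against.** The strongest reply is that the measurement itself is protected. The patient writes the score and is not told the allocation until 4 to 6 weeks, after the 10-day diary has ended. Administrators teach the questionnaire and collect it, the forms are scanned, the paper is locked away, and access runs through the principal investigator. Masked analysis and data lock are often set out in a SAP or data-management plan, neither of which is shown. Most of this stands, and it keeps the point moderate. It does not remove it, because the protocol states an access rule that admits the surgeons, and a SAP could add masking without changing that rule.

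A reader might infer four stronger things that the documents do not support:

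- **That the surgeons know every allocation.** Each is certain to know only the patients they operated on.
- **That they can edit scores unnoticed.** The rule grants entry and analysis. Editing is an inference, and the scans and originals would make changes detectable if someone compared them.
- **That sections 8.2 and 9.2 flatly contradict each other.** Assisting or validating need not require file rights; a statistician could check output or receive an extract. It is an omission to reconcile.
- **That a few misread marks would overturn the result.** That follows only for an analysis split at 7.5, from a selected starting table. The 7.5 cut appears only in the sample-size text (3.1 and 9.1), and a rank test responds little.

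**Conclusion.** The point holds as a design weakness that should be corrected. The protocol grants entry and analysis rights over the primary VAS to people who know the arm of the patients they operate on, calls the trial double-blind, and describes blinding of the patient alone. The exposure lies in transcription and in analysis choices, not in how pain is scored. Existing safeguards reduce it, but no check that would make them effective is stated.

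No numerical bias can be derived from the documents, and none is claimed. The planned 64 per arm is not affected. The conclusion assumes that the access rule means what it says and that no unseen document withdraws the surgeons' rights. It does not assume or suggest that anyone would misrecord data.

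**What to change.** In sections 8.2, 12.2 and 14:

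- Restrict VAS entry to existing research administrators who did not handle the allocation, and give procedurists no entry rights over the VAS.
- Keep the VAS pages apart from the intraoperative procedure details, so that the person entering scores cannot see the procedure. Changing file permissions alone is not enough: the two now share a package, which is collected at the visit where the allocation is disclosed.
- Add the biostatistician to the access list, with arms coded A and B.
- Check the VAS data against the existing scans and lock them before the codes are revealed.

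In section 4, state who besides the patient is blinded, or drop the double-blind label.

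Cost: the administrators, the biostatistician and the scans are already in the plan, and the sample size is unchanged. The package must be split into two parts, the comparison with the scans takes some administrator time, and co-investigators must wait for the lock before they see results by arm.

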## **9 SAMPLE SIZE AND STATISTICAL METHODS**

### **9.1 Determination of Sample Size**

Based on previous studies, as well as unpublished results from surgeons who have performed LAH around the South East Asian region, we are expecting 50% of the patients in the COH arm to have a VAS score of more than 7.5. We expect to see 25% patients in the LAH arm having a VAS score of more than 7.5.

With a power of 80%, chance of type 1 error (alpha) less than 5% and accounting for 10% of loss to follow up rate, the sample size required for the study to be adequate powered is having 64 patients in each arm (N=128).

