### **2.2 Primary Objectives**

Daily visual analogue pain scale (VAS) in the first 10 days after surgery.

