## **3 STUDY POPULATION**

### **3.1 List the Number and Nature of Subjects to be Enrolled**

Based on previous studies, as well as unpublished results from surgeons who have performed LAH around the South East Asian region, we are expecting 50% of the patients in the COH arm to have a VAS score of more than 7.5. We expect to see 25% patients in the LAH arm having a VAS score of more than 7.5.

With a power of 80%, chance of type 1 error (alpha) less than 5% and accounting for 10% of loss to follow up rate, the sample size required for the study to be adequate powered is having 64 patients in

each arm (N=128).

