### **3.5 Subject Replacement**

Subjects who drop out are accounted for in the sample size calculation and will not be replaced.

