## **15 FUNDING and INSURANCE**

En-Life has agreed to sponsor 40 laser probes to initiate the study. Grants will be applied to cover the remaining cost of the other 14 laser probes. En-life has agreed to loan the Laser Generator for free. Singhealth research indemnity insurance – for utility to cover for the management of any complications during the trial

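### The stated 80% power after 10% loss does not hold for the Fisher exact test in Section 9.2, which gives about 76.5% on average

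*Protocol*

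**What the plan says.** Sections 3.1 and 9.1 carry the same sizing text. The event is a VAS score above 7.5: "we are expecting 50% of the patients in the COH arm to have a VAS score of more than 7.5", against 25% in the LAH arm. The operating conditions are "With a power of 80%, chance of type 1 error (alpha) less than 5% and accounting for 10% of loss to follow up rate", and the result is that "the sample size required for the study to be adequate powered is having 64 patients in each arm (N=128". No formula, test or sidedness is given for this calculation.

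Section 3.5 closes the route to topping up: "Subjects who drop out are accounted for in the sample size calculation and will not be replaced".

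Section 9.2(a) fixes the tests at p < 0.05. For proportions, "All categorical data would be analysed using the Fisher Exact Test". For measurements, "All continuous variables would be analysed using the Mann-Whitney U test".

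The primary objective in Section 2.2 is worded as "Daily visual analogue pain scale (VAS) in the first 10 days after surgery", with no mention of the 7.5 cut-off.

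**The concern.** VAS above 7.5, yes or no, is a categorical outcome, so under Section 9.2 the comparison used for sizing goes to Fisher's exact test. Fisher is conservative at these sample sizes: its true type 1 error lies well below 5%, and it loses power accordingly. If 64 per arm came from a formula for a less conservative test, the 10% allowance for loss is used up by the choice of test, and nothing is left to cover patients who actually drop out. The trial would then have a larger chance of missing the assumed effect than the protocol tells the ethics board and funders. With replacement ruled out, the protocol has no way to recover that power later.

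**Working it through.** **Inputs, all from the protocol.** Event rates 0.50 (COH) and 0.25 (LAH), power 80%, alpha 5%, loss 10%, 64 per arm (Sections 3.1 and 9.1); 1:1 allocation (4.1); no replacement (3.5); Fisher's exact test at p < 0.05 (9.2). One assumption is added: the test is two-sided.

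**Step 1: reproduce the 64.** The two-sided, uncorrected, pooled-variance formula is

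n = [1.960·√(2·p̄·(1−p̄)) + 0.842·√(p₁(1−p₁) + p₂(1−p₂))]² / (p₁−p₂)², with p̄ = 0.375.

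- First term: 1.960 × √0.46875 = 1.342
- Second term: 0.842 × √0.4375 = 0.557
- n = (1.342 + 0.557)² / 0.0625 = 57.67, so 58 evaluable per arm
- Allowing for loss: 57.67 / 0.9 = 64.08. Rounding to 58 first gives 58 / 0.9 = 64.4, hence 65; that difference is immaterial.

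So 64 is what an uncorrected chi-square (z) calculation gives. The two-sided continuity-corrected version gives 74 after inflation. One-sided versions give 52, or 60 with correction. The two-sided reading is therefore the one that fits.

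**Step 2: power of the planned test.** For evaluable arm sizes n₁ and n₂,

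power = Σₓ Σᵧ Bin(x; n₁, 0.50) · Bin(y; n₂, 0.25) · 1[two-sided Fisher p(x, y) < 0.05],

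summed over every possible outcome.

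| COH / LAH evaluable | Fisher power |
|---|---|
| 64 / 64 (no loss) | 80.2% |
| 58 / 58 | 74.3% |
| 57 / 57 | 73.2% |
| 57 / 58 | 77.3% |
| 58 / 57 | 76.1% |
| 56 / 59 | 77.4% |
| 59 / 56 | 75.8% |

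The jumps between neighbouring splits come from the discreteness of the test, which is worst when the arms are equal.

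**Step 3: average over the loss.** Since no one can know the final split in advance, weight each (n₁, n₂) by independent Binomial(64, 0.9) retention in each arm. Average Fisher power is 76.5%. If exactly 12 or 13 of the 128 are lost, split at random, it is 76.2% or 76.6%. Fisher reaches 80% in only about 2% of random-loss outcomes. With 5% loss the average is 79.2%.

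**Step 4: other tests under the same 10% loss.**

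| Test | Average power | Maximum exact size at 57–58 per arm |
|---|---|---|
| Fisher | 76.5% | 3.2–4.1% |
| Boschloo | 79.7% | 4.7–5.0% |
| Uncorrected chi-square | 80.3% | 5.3–5.5% |

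**Step 5: what Fisher would need.** Average power after 10% loss, by number randomised per arm: 68 gives 79.7%, 69 gives 80.5%, 70 gives 81.2%.

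**The case against.** **The stated number is not an arithmetic slip.** This stands. For an uncorrected chi-square test, 64 per arm is right. The fault is that Section 9.2 plans a different, more conservative test. Because the protocol gives no formula, the source of the 64 is an inference; the power of Fisher's test at that size is not.

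**Fisher may not be the primary test at all.** Section 2.2 names daily VAS, the cut-off of 7.5 appears only in the sizing text, and Section 9.2 sends continuous variables to Mann-Whitney. This is the strongest point, and it limits the finding to the comparison used for sizing. It does not rescue the 80%, which would then describe no planned test: the protocol gives no mean or standard deviation from which Mann-Whitney power could be worked out.

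**The gap is small beside the uncertainty in the inputs.** This is true. If the LAH rate were 24% rather than 25%, Fisher would average 80.2% after 10% loss; at 27% it would average 68.3%. But a sizing statement has to be correct for the inputs it declares, and this one is not.

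**The interim looks at 50% and 75% matter more for type 1 error.** They are left out of the figures above. If alpha is set aside for them, power falls further. If they are unadjusted, the difference in size between Boschloo and chi-square is a lesser issue. Neither case makes the stated 80% correct.

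**The test could be one-sided.** One-sided Fisher would give 84.2% at 58 per arm, but no one-sided calculation leads to 64.

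**Conclusion.** The concern holds. Taking the protocol's own rates, loss and significance level, and a two-sided test, Fisher's exact test on VAS above 7.5 has 76.5% power on average, not 80%. The chance of missing the assumed effect is therefore about 23% to 24% instead of 20%. The shortfall is about 3.5 points on average and 3 to 7 points across the splits of 57 and 58 per arm. The average assumes loss that is random and independent of arm. The result covers only the comparison used for sizing. It is a modest defect, but it sits in the protocol's central sizing statement and should be corrected.

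**What to change.** In Sections 3.1 and 9.1, state which comparison, which test and which sidedness the power refers to. Then take one of these routes:

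- **(a) Keep Fisher and 128 patients.** Restate power as about 76% after 10% loss, with 73% to 74% if the arms end exactly equal. This is wording only, at the price of declaring a lower power.
- **(b) Keep 128 patients and about 80%.** Name Boschloo's exact unconditional test for the VAS above 7.5 comparison, as an exception to the general rule in 9.2. This is wording only, after checking that the chosen software offers the test. Uncorrected chi-square would also give about 80%, but its exact size of 5.3% to 5.5% exceeds the stated alpha of below 5%, and that would have to be accepted openly.

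Keeping both Fisher and 80% needs 69 per arm, 138 in total, or 10 more patients. As 138 does not fill blocks of four, 70 per arm (140, or 12 more) is the practical figure.

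If daily VAS by Mann-Whitney is the intended primary analysis, say so and do not attach the 80% to it without a calculation for that test.

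A separate minor point with no bearing on power: Section 15 counts 40 sponsored laser probes and adds that "Grants will be applied to cover the remaining cost of the other 14 laser probes", which makes 54 for 64 LAH patients. If one probe is used per patient (an assumption), the two numbers need reconciling.
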